The primary endpoint is the % reduction in 2-hour incremental AUC for glucose. Using the t-distribution with 2-tailed $p<0.05$ and assuming an average CV of within-individual variation of 2-hour incremental AUC values of 25%, $n=20$ subjects (10 lean and 10 overweight) has 80% power to detect a 17% difference in AUC, 90% power to detect a difference of 19% and 99% power to detect a difference of 26%. Within each subject group ($n=10$) there is 80% power to detect a difference in AUC of 25%, and 80% power to detect a 33% difference between the responses of lean and overweight subjects. To allow for 10% dropout, we will recruit $n=11$ lean and $n=11$ overweight subjects.

Subject Recruitment

Participants will be recruited from the pool of participants at GI Laboratories who have indicated that they are willing to be contacted and asked if they wish to participate in new studies. If an insufficient number of subjects can be recruited, then a newspaper advertisement will be used to recruit new subjects.

Selection of participants

Participants willing to be considered will be invited to come to the research centre to have the study procedures explained to them and be given a copy of the consent form which they may either sign then, take away to sign at a later date, or decline to participate. Participants will be encouraged to ask any questions they may have and not to sign the consent form until all of their questions have been answered to their satisfaction. Those who consent to participate will come to the research centre for a pre-selection visit when subject eligibility will be determined. During this visit, the 10-14hr overnight fasted participants will complete a questionnaire (Appendix 1) to assess medical history, and lifestyle factors, have height, weight, waist circumference and blood pressure measured, and have a blood sample drawn for measurement of glucose, HbA1c, lipids, creatinine, AST, ALT and complete blood count. Females will have a pregnancy test.

PROCEDURES

The study will have a randomized block design with repeated measures. One block, which will be double-blinded, will test the effect of Axulin capsules; the other block, which will be open label, will test the effect of Axulin tablets. Within each participant, the order of the blocks will be randomized and within each block the order of the treatments will be randomized.

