Eligible participants will be instructed to maintain stable dietary and exercise habits and for the duration of the study, to avoid vigorous physical activity for 24hr before each visit and to and consume their normal dinner the night before each visit. At each visit current use of medications and natural health products participants will be reviewed with each participant and any changes will be discussed with the investigator. Female participants will be advised that if they become pregnant during the study they are to contact the investigators and discontinue their participation immediately.

Each subject will be studied on 6 separate days with at least a 3-day interval between tests. On each test day, subjects will come to GI Labs ([name]) in the morning after a 10-14h overnight fast. On each test occasion the subject will be weighed, and give fasting finger-prick and venous blood samples. Blood from a forearm vein will be collected into a 6ml EDTA tube (Vacutainer, BD Canada, Mississauga, ON). Finger-prick blood samples will be collected into 2 separate vials: one (2-3 drops blood into a fluoro-oxalate tube) for glucose analysis and the other (6-8 drops of blood into an 0.3ml Microvette with clot activator, Sarsted, Germany) for insulin. After the fasting sample the subject will take 12 capsules or 2 tablets with a drink of 250ml water. Subjects will rest for 3-10min and have their blood pressure measured; 40min after swallowing the first capsule or tablet a finger-prick blood sample (2-3 drops for glucose and 6-8 drops for insulin analysis) will be collected and then subjects will consume 82.5g dextrose (containing 75g anhydrous glucose) dissolved in 300ml water within 5min plus a drink of 150ml water within 10min of starting the glucose drink. Further finger-prick blood samples for glucose (2-3 drops) and insulin (6-8 drops) will be obtained at 15, 30, 45, 60, 90 and 120 min after starting to drink the glucose solution. Venous blood samples (7ml) will be collected after the 60 and 120 min finger-prick. During the test subjects will remain seated quietly except for trips to the washroom if necessary. After the last blood sample subjects will be offered a snack and be free to leave.

Treatments

The 6 treatments administered will consist of the following:

- 12 placebo capsules with 250ml water (0g Axulin)
- 250ml water alone (0g Axulin)

- 4 placebo and 8 Axulin capsules (2g Axulin)
- 16 Axulin capsules (4g Axulin)

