24	Overweight	A	C	B	F	E	D
25	Overweight	B	C	A	E	F	D
26	Overweight	C	A	B	D	F	E

27	Overweight	B	C	A	F	D	E
28	Overweight	D	F	E	B	A	C
29	Overweight	D	E	F	C	B	A
30	Overweight	F	E	D	A	B	C
31	Overweight	A	C	B	E	F	D
32	Overweight	E	D	F	C	A	B

Instructions: please assign capsules to codes A, B or C, and tablets or empty bag to codes D, E or F. Place treatment assignments into a sealed opaque envelope and keep the envelope in an accessible location. Treatments are as follows:

BLOCK 1 (A, B or C)

- Placebo 1; 16 Placebo capsules
- 2g Axulin caps: 4 Placebo capsules plus 8 Axulin capsules
- 4g Axulin caps: 16 Axulin capsules

BLOCK 2 (D, E or F)

- empty bag
- 2g Axulin tablets: 2 Axulin tablets
- 4g Axulin tablets: 4 Axulin tablets

Biochemical Analysis

Finger-prick blood samples for glucose analysis will be placed in the refrigerator immediately after being obtained and at the end of the test placed in a -20°C freezer until analysis which will be performed within 5 days. Glucose analysis is done using an YSI model 2300 STAT analyzer (Yellow Springs, OH). The microvette tubes used to collect blood for insulin analysis will be centrifuged at 3622×g for 2 min and the serum transferred to labeled polypropylene tubes and stored at -20°C prior to analysis of insulin using the Human Insulin EIA Kit (Alpco Diagnostics). Venous blood samples will be stored at 4°C until the end of the study after which they will be centrifuged at ~1400×g for 10 min and the plasma removed and separated into 2×1ml aliquots; 1 for analysis of triglycerides at St. Michael's Hospital biochemistry laboratory and the other for measurement of the active ingredient in Axulin by liquid chromatography/mass spectrometry.

Statistical Analysis

Incremental areas under the blood glucose, insulin and triglyceride response curves (AUC), ignoring area below fasting, will be calculated. Blood glucose and insulin concentrations and AUC values will be analyzed using repeated measures ANOVA examining for the main effects of dose, form (tablets vs capsules) and subject group (lean vs overweight) and their interactions. After demonstration of significant heterogeneity, differences between individual means will be assessed using Tukey's test to adjust for multiple comparisons.

Informed Consent

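### The AUC model has no covariate for the pre-dose fasting value taken at each visit; adding one may improve precision, by an amount the documents cannot fix

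*Combined protocol and SAP*

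**What the plan says.** The Number of subjects section states: "The primary endpoint is the % reduction in 2-hour incremental AUC for glucose". It sizes the trial "assuming an average CV of within-individual variation of 2-hour incremental AUC values of 25" per cent, and reports that n=20 "subjects (10 lean and 10 overweight) has 80% power to detect a 17% difference in AUC".

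Under PROCEDURES, each subject attends six test days. The fasting samples come before the product: "On each test occasion the subject will be weighed, and give fasting finger-prick and venous blood samples". Part of the finger-prick blood goes to glucose and part to insulin. A second finger-prick sample follows 40 min after dosing starts, just before the glucose drink.

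The Statistical Analysis section computes incremental areas and discards area below fasting. Its only model is this: "AUC values will be analyzed using repeated measures ANOVA examining for the main effects of dose, form (tablets vs capsules) and subject group", plus interactions, with Tukey's test for pairs of means. No baseline covariate is named anywhere. The section does not say which of the two samples taken before the glucose drink is the fasting reference.

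**The concern.** Incremental AUC subtracts the fasting value from every later point. Over 120 minutes this fixes the adjustment slope at about -120 min per mmol/L (ignoring the truncation below fasting). That slope is the best one only if post-glucose values move one-for-one with that morning's fasting value. If part of the fasting deviation is assay error, or variation that later samples do not share, it passes into the AUC with the sign reversed. A fasting reading that is high by chance then gives a low AUC.

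Comparing treatments within a subject removes that person's average fasting level, but not these visit-level deviations. A covariate with an estimated slope could take out what subtraction leaves behind, using data already collected. The same reasoning applies to insulin AUC and fasting insulin.

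What is at stake is the width of the intervals on the dose, form and subgroup contrasts in a 20-subject trial. Validity is not in question.

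**Working it through.** **Inputs from the Number of subjects section.** CV 25%; two-sided 0.05; t-distribution; n=20 (10 lean, 10 overweight); 17% at 80% power; 25% at 80% power within a group of 10. The 33% target is in OBJECTIVES.

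**Input not in the documents.** rho, the absolute within-subject correlation between a visit's fasting value and its incremental AUC. It is an assumption, examined from 0 to 0.5.

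**Step 1: reproduce the plan.** Detectable difference = SD/√n × (t(0.975, n−1) + t(power, n−1)), with 25% as the SD of the paired difference. For n=20 at 80% power: 25/√20 × (2.093 + 0.861) = 5.590 × 2.954 = 16.5%, stated as 17%. At 90% power the result is 19.1% (stated 19%). Within n=10 it is 24.9% (stated 25%). The plan's figures reproduce. By the noncentral t, exact power is 82.2% for 17% at n=20 and 80.3% for 25% at n=10.

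**Step 2: add the covariate.** Residual SD = 25 × √(1 − rho²), with one degree of freedom lost (19 to 18; 9 to 8). Example at rho 0.3: SD = 25 × √0.91 = 23.85; noncentrality = 17/(23.85/√20) = 3.19; power 85.4%.

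| rho | variance removed | power, 17%, n=20 | power, 25%, n=10 |
|---|---|---|---|
| no covariate | – | 82.2% | 80.3% |
| 0 | 0% | 82.0% | 79.1% |
| 0.1 | 1% | 82.4% | 79.5% |
| 0.2 | 4% | 83.5% | 80.6% |
| 0.3 | 9% | 85.4% | 82.6% |
| 0.5 | 25% | 91.3% | 89.1% |

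A 5-point gain at n=20 needs rho of about 0.37 or more. The difference detectable at 80% power with n=20 goes from 16.5% without the covariate to 15.8% at rho 0.3 and 14.3% at rho 0.5.

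**Step 3: what could produce rho.** If a share b of the fasting deviation is carried into the later values, then |rho| ≈ (1 − b) × 120 × s / (0.25 × mean AUC), where s is the within-subject fasting SD. Neither s nor the mean AUC is in the documents. With assumed values s = 0.2 mmol/L and mean AUC = 200 mmol·min/L: 120 × 0.2/50 = 0.48 with no tracking, 0.24 with half tracking, and 0 with full tracking.

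**Step 4: the 33% target.** For one paired contrast at n=20 without the covariate, power is already about 99.9% with SD 25%. If the 25% is instead a per-visit CV, the SD of a difference is √2 × 25 = 35.4% and power is still about 98%.

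**Step 5: Tukey-adjusted pairs.** Assume that Tukey's test covers all six treatment means with (20 − 2) × (6 − 1) = 90 pooled error degrees of freedom and a paired SD of 25%. Power for a 17% difference is then about 55% unadjusted, 61% at rho 0.3 and 72% at rho 0.5.

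**The case against.** The strongest reply is that incremental AUC already uses the fasting value. If post-glucose levels shift one-for-one with fasting, subtraction has removed the variation, rho is zero and the covariate only costs a degree of freedom. The plan also limits visit-to-visit variation through a 10-14h fast, stable diet and no vigorous activity for 24hr. Nothing in the documents says where between full and no tracking this trial lies. In the n=10 groups a weak covariate slightly lowers power. All of this stands.

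A reader might infer that power is certainly being given away, or that the stated power is too high. The documents support neither. The first needs a value of rho that they do not give. The second fails because the CV is defined on the incremental AUC itself, so any fasting noise is already in the planning variance. Nor is there a bias: the planned ANOVA is not invalid for lack of this covariate.

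It is also fair to say that a single contrast at the 33% target has power to spare. That does not dispose of the point, because the plan also sizes itself on 17% and 25% differences, compares lean with overweight subjects and capsules with tablets, and tests pairs with Tukey's adjustment.

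Finally, the mechanism assumes that the pre-dose sample is the AUC baseline. If the 40-min sample is meant, the gain could be smaller.

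**Conclusion.** The point holds as an optional, low-cost gain in precision of uncertain size. The covariate is available at every visit and the planned model leaves it out. Over an assumed rho of 0.1 to 0.5, the change in power is +0.2 to +9.1 points for 17% at n=20 (82.2% to 82.4%–91.3%) and −0.8 to +8.8 points for 25% at n=10 (80.3% to 79.5%–89.1%). It is negligible for one contrast at 33% and matters more for smaller, subgroup or Tukey-adjusted contrasts.

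These figures take 25% as the SD of the paired difference, as the plan's own numbers imply, and the pre-dose sample as the AUC baseline. The upper end should not be read as an expected gain.

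**What to change.** In the Statistical Analysis section, before unblinding:

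- Add each visit's pre-dose fasting glucose as a covariate in the glucose AUC model, and pre-dose fasting insulin in the insulin AUC model.
- Enter it as the deviation from the subject's own mean over the visits, so that the lean-versus-overweight comparison is unchanged.
- State that the 40-min sample is not the covariate, because it is taken after the product and may carry a treatment effect. Name the sample that defines the AUC baseline.
- Report the unadjusted ANOVA as a sensitivity analysis.

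The cost is wording and one degree of freedom per model, with no extra subject, visit or sample. If rho is near zero, the loss is 0.2 points of power at n=20 (82.2% to 82.0%) and about 1 point in the n=10 groups (80.3% to 79.1%).

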Pre-diabetes and Type II diabetes involve an impaired post-receptor response to insulin that hinders the glucose uptake response after meal consumption.¹⁷⁻¹⁹ Chronic hyperglycemia and the resulting compensatory hyperinsulinemia promote a cohort of acute and chronic sequelae including cardiovascular disease, liver complications, central nervous system degeneration and hyperglycemic osmotic stress.²⁰⁻²³ Axulin is a natural health product consisting of a mixture of extracts from herbs and vegetables present in normal diets which was identified by screening more than 100,000 compounds and extracts in a patented cell-culture based assay system targeting the IRS proteins. In vitro, Axulin has marked effects on the IRS-2 branch of the insulin signaling cascade to enhance downstream insulin signaling. Axulin has been shown in animal models to increase glucose uptake in peripheral tissues and decrease circulating blood glucose and triglyceride concentrations. Regular supplementation of the diet with Axulin would be expected to reduce the incidence of associated pre-diabetic and diabetic complications, resulting in an increased quality of life for patients without resorting to current anti-diabetic prescription drugs such as metformin and others that may have substantial unwanted side effects in patients.

HYPOTHESES

Axulin will reduce postprandial glucose and insulin responses in a dose-dependent fashion in healthy subjects without diabetes. The reduction in glucose and insulin will be relatively greater in insulin-resistant than insulin-sensitive subjects.

OBJECTIVES

The primary objective of this study is to determine the dose of Axulin which will reduce the incremental area under the blood glucose response curve (AUC) elicited by 75g oral glucose in healthy subjects by $\geq 33\%$.

The secondary objectives are to determine the dose-response effects of Axulin on:

- blood glucose and serum insulin AUC
- % reduction of insulin AUC
- the blood glucose and serum insulin increments at 15, 30, 45, 60, 90 and 120min
- insulinogen index
- Matsuda insulin sensitivity index
- ISSI-2 index of beta-cell function
- incremental blood lipid response at 120min
- plasma triglyceride response
- plasma axulin response

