The other objectives are to determine whether the effects of Axulin on glucose, insulin and triglyceride responses differ in lean vs overweight subjects and to determine whether the effects of Axulin on postprandial responses are similar when administered in capsule versus tablet form.

SUBJECTS

Inclusion criteria

Subjects will be males or non-pregnant, non-lactating females aged 18-60 years who have no history of diabetes and are in good health. Lean subjects will have a BMI >18.5 and $<25.0\text{kg}/\text{m}^2$, overweight subjects will have a BMI ≥ 25.0 and $<35.0\text{kg}/\text{m}^2$. Subjects taking stable doses (for at least 4 weeks of signing the consent form) of the birth control pill, thyroxin replacement therapy, statins, fibrates, cholesterol absorption inhibitors, anti-hypertensive medications, aspirin, non-steroidal anti-inflammatories and/or mild anxiolytics or sedatives can be included.

Female subjects of child-bearing potential must, for the duration of the study, be using one of the following birth control methods: total abstinence, a hormonal birth control method (oral, injectable, transdermal, or intra-vaginal), intrauterine device, or confirmed successful vasectomy of partner.

Exclusion criteria

- Fasting serum glucose $>6.9\text{mmol}/\text{L}$ (124mg/dL)
- HbA1c $>6.4\%$
- Fasting serum triglycerides $>4.5\text{ mmol}/\text{L}$ (399 mg/dL)
- Fasting LDL cholesterol $>4.99\text{ mmol}/\text{L}$ (192 mg/dL)
- Blood pressure >149 systolic or >89 diastolic
- Serum creatinine, or aspartate- or alanine transaminases >1.2 times upper limit of normal
- White cell count, red blood cell count, hemoglobin or hematocrit outside normal range
- Hospitalization for surgery or a medical condition within 3 months of signing the consent form

- Use of any drug to treat diabetes
- Use of medications other than those listed above or the presence of any condition which might, in the opinion of [name], either: 1) make participation dangerous to the subject or to others, or 2) affect the results
- Allergy or sensitivity to tarragon, chromium, escarole, lettuce, microcrystalline cellulose, inulin, food colouring (FD&C Yellow#5 and Blue#1) or vegetable-based capsules (silicon dioxide, titanium dioxide, hydroxypropylmethylcellulose)

Number of subjects

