- 2 Axulin tablets (2g Axulin)
- 4 Axulin tablets (4g Axulin)

Each placebo capsule contains 250mg inulin, each identical-looking Axulin capsule contains 250mg Axulin. It is anticipated that Axulin will be sold in tablets because 1g can be compacted into a tablet without loss of biological activity, but, because Axulin is a low-density powder, only 400mg can be placed in a capsule of similar size. We will use capsules in this study because it is more economical to produce the relatively small number of identical-looking placebo capsules required as compared to producing placebo tablets. To obtain doses in 1g increments, we will use smaller capsules containing 250mg each. The rationale for including tablets in the study is that Axulin in tablet form might be more slowly bioavailable than when encapsulated; thus, it is

important to determine whether the effects of Axulin tablets on postprandial responses is similar to the same dose taken in capsules.

Blinding

The number of Placebo and Active Axulin capsules and tablets required for the study will be provided to GI Labs. A person not involved in any other aspect of the study will make up 6 small zip-lock plastic bags for each subject labelled with a subject number and visit number and containing the treatment for visits 1 through 6 (the bag for the water alone treatment will be empty). The treatments will be randomized as shown in Table 1. The order of the blocks and the order of the treatments within each block were randomized using the @rand() function of Excel with 2 blocks of 6 created for lean subjects and 2 blocks for overweight subjects; the 2 extra orders are for use in case of drop-outs so that at least n=20 subjects complete the study (see Table 1). The person labeling and filling the bags with the treatments will assign the treatments to the codes and place the treatment assignments in a sealed opaque envelope kept in an accessible location. The envelope will be opened only after the study has been completed and the database locked, or in case of emergency if required for participant safety.

Table 1: Randomization Scheme

ID	Group	Visit 1	Visit 2	Visit 3	Visit 4	Visit 5	Visit 6
1	Lean	A	B	C	E	D	F
2	Lean	B	C	A	E	F	D
3	Lean	F	D	E	C	A	B
4	Lean	B	A	C	F	E	D
5	Lean	D	E	F	A	C	B
6	Lean	D	F	E	C	B	A
7	Lean	F	D	E	A	C	B
8	Lean	C	B	A	D	E	F
9	Lean	D	F	E	B	C	A
10	Lean	C	A	B	E	D	F
11	Lean	B	A	C	E	F	D
12	Lean	F	E	D	A	B	C
21	Overweight	D	E	F	C	B	A
22	Overweight	F	D	E	B	A	C
23	Overweight	A	B	C	E	D	F

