The GI Testing protocol has been approved by the Western Institutional Review Board® which meets all requirements of the US Food and Drug Administration (FDA), the Department of Health and Human Services (DHHS), the Canadian Health Protection Branch (HPB), Canadian

Institutes for Health Research (CIHR) and the European Community Guidelines. Informed consent is obtained from all subjects for each series of tests they participate in.

Participant Withdrawal Criteria

The Investigator may elect to withdraw the participant from the study or the participant may withdraw from the study at any time. Reasons for withdrawing include, but are not limited to:

- Development of an exclusion criterion during the course of the study
- Study product never consumed
- Participant was lost to follow-up
- Participant did not follow study procedures
- Participant elected to withdraw from the study for any reason
- Investigator elected to remove participant from the study for any reason
- Subject takes longer than the specified time to complete the study

In the case of premature withdrawal, all planned assessments for the end of the study visit will be completed and the sponsor will be informed as soon as possible. The subject's Case Report Form ("CRF") will be completed including the final assessment. The date and main reason for the premature withdrawal will be clearly documented in the subject's file and written down on the CRF

ADVERSE EVENT REPORTING

An adverse event (AE) is any symptom, injury, illness, or medical/surgical procedure whether planned or not or whether associated with the study foods or not. AEs will be assessed at each visit and recorded in the Case Report Forms. AEs will be evaluated for duration, severity, seriousness, and causal relationship to the food items provided in the study by the study physician who will decide if any action is required and provide referral, treatment, and/or follow-up as appropriate until resolved, judged to no longer be clinically significant, or if a chronic condition, until fully characterized. Research staff will record the final outcome and resolution date of the event wherever possible. The action taken and the outcome will be recorded in the Case Report Form.

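### A mixed model on all completed test days would use partial data that a classical repeated measures ANOVA drops; the expected gain is small and the priority low

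*Combined protocol and SAP*

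**What the plan says.** - **Model.** The Statistical Analysis section states that "AUC values will be analyzed using repeated measures ANOVA examining for the main effects of dose", form (tablets or capsules), subject group (lean or overweight) and their interactions, followed by Tukey's test.
- **Test days.** Under Procedures, each participant attends six test days, one per treatment.
- **Sample size.** It is counted in people who finish. Number of subjects says "To allow for 10% dropout, we will recruit" 11 lean and 11 overweight. The Blinding section adds that "the 2 extra orders are for use in case of drop-outs so that at least n=20 subjects complete the study".
- **Withdrawal.** Participant Withdrawal Criteria lists reasons for withdrawal and asks for end-of-study assessments, a completed case report form, and the date and main reason. It does not say whether test days already completed enter the analysis.
- **Analysis set.** No analysis set or missing-data rule appears in the available text. The opening part of the document was not available to this review.

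**The concern.** Classical repeated measures ANOVA works on a complete participant-by-treatment table. A participant who stops after visit 5 then contributes nothing, although five glucose tolerance tests have been done. Counting the sample size in completers fits that reading but does not establish it.

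Two things could be at stake. The first is precision, because valid test days are discarded. The second is bias, if those who leave respond differently from those who stay. The plan gives some reason to ask about the second. One withdrawal reason is "Development of an exclusion criterion during the course of the study", the exclusion criteria include a limit on "Fasting serum glucose", and the Hypotheses section expects that "The reduction in glucose and insulin will be relatively greater in insulin-resistant than insulin-sensitive subjects". Without a stated rule, the handling of partial data could also be settled after the results are known.

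**Working it through.** **Inputs from the plan (Number of subjects).** Two-sided 5% t-test, CV 25%, 20 completers, 22 recruited, 80% power for a 17% difference.

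**Inputs assumed.**
- 2 of 22 withdraw, which is the plan's allowance of about 10%.
- The SD of a within-person difference is 25 points, which reproduces the plan. The alternative is 25 × √2 = 35.4 points, if 25% is the single-day CV.
- Between-person SD is 25 to 50 points, with a random participant intercept only.

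**1. The plan's own figure.** Detectable difference = (t₀.₉₇₅,₁₉ + t₀.₈₀,₁₉) × SD/√n = (2.093 + 0.861) × 25/√20 = 2.954 × 5.59 = 16.5, stated as 17. Noncentral-t power at 17 points is 0.822.

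**2. Test days recovered.**
- Both stop after visit 5: 20×6 + 2×5 = 130 completed days, of which completers-only drops 10 (7.7%).
- Both stop after visit 3: 126 days, 6 dropped (4.8%).
- Both stop after visit 1: 122 days, 2 dropped (1.6%).

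**3. Precision, if withdrawal is unrelated to response.** Both analyses are unbiased. Generalised least squares was applied to the Table 1 orders for the first 11 IDs in each group, with one lean and one overweight participant withdrawn, and averaged over random assignments of treatments to codes. The contrast is 4 g versus placebo capsules, with SD of a difference 25. The completers SE is 25/√20 = 5.59. The mixed-model SE is 5.59 × √(variance ratio).

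| Both stop after | Variance reduction | SE | 17/SE | Power at 17 points |
|---|---|---|---|---|
| completers only | – | 5.59 | 3.04 | 0.82 |
| visit 1 | about 0.5% | 5.58 | 3.05 | 0.83 |
| visit 2 | about 2.5% | 5.52 | 3.08 | 0.83 |
| visit 3 | about 5% | 5.45 | 3.12 | 0.84 |
| visit 5 | 7–8% | about 5.37 | 3.17 | 0.85 |

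Power uses 19 df for completers and 20 for the mixed model. With SD 35.4 the completers SE is 7.91, and power rises from 0.53 to at most 0.57.

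**4. Bias, only if withdrawal is related to response.** Suppose the people lost have a true 4 g reduction larger than the others' by d points. The documents give no value for d; 10 to 30 is an illustration.
- Two overweight participants lost: completers understate the overall reduction by 2d/22 = d/11, or 0.9 to 2.7 points, and the overweight reduction by 2d/11, or 1.8 to 5.5 points.
- One overweight participant lost, closer to the plan's allowance of one per group: d/22, or 0.45 to 1.4 points overall, and d/11, or 0.9 to 2.7 points in the overweight group.
- The mixed model removes about 81–84% of this bias for stops after visit 5, 53–59% after visit 3, about 30% after visit 2 and 4–7% after visit 1.

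A different mechanism was also simulated: the two participants with the most extreme AUC on their first 4 g day withdraw. Completers-only was off by about 0.7 points (single-day SD 17.7) to 1.4 points (single-day SD 25). The mixed model stayed near the true 17.0. When withdrawal followed only a person's overall glucose level and the effect was the same in everyone, neither analysis was biased.

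**The case against.** **Completers-only is not written in the plan.** This stands. An ANOVA with participant as a factor can be run on incomplete data, and the spare orders safeguard recruitment without defining an analysis set. The supportable statement is that the named method, in its usual form, drops partial data and the available text gives no other rule.

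**Precision is already protected.** This largely stands. With 20 completers, power for 17 points is 0.82, so the mixed model adds at most about three percentage points, and almost nothing if people leave early.

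**A reader might infer that the withdrawal rules bias the primary result.** The documents do not support this:
- Fasting samples are taken at every visit ("On each test occasion the subject will be weighed, and give fasting finger-prick and venous blood samples"), but no section says that test-day glucose is compared with the exclusion limit.
- The limit is a serum value at screening, whereas test-day glucose is measured in finger-prick blood. Under Biochemical Analysis those samples are frozen and analysed within 5 days, while visits may be 3 days apart. A high value may be unknown at the next visit.
- Blood pressure is also an exclusion criterion and is known at once, but nothing in the plan ties it to glucose response.
- One must then assume that those withdrawn are more insulin-resistant and that the untested hypothesis is true. Someone who crosses the glucose limit has arguably also left the healthy population named in the objective.

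**A reader might also suspect selective withdrawal.** The documents do not support that either. "The envelope will be opened only after the study has been completed and the database locked", emergencies aside, and the reason for each withdrawal is recorded. The tablet block is open label, so the blinding covers only the capsule block, but that is not evidence of selection.

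**Conclusion.** The point holds as a low-priority improvement. A concrete method that uses the planned factors and all data collected is preferable to one that, in its classical form, discards participants with any missing test day. With 2 of 22 withdrawn, the expected gain is a variance reduction of about 0.5% to 8%, and power at 17 points of 0.83–0.85 instead of 0.82. These figures assume an SD of a difference of 25 and a random-intercept model. They were not computed for the richer covariance recommended below.

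Protection against response-related withdrawal is a possible and partial side benefit: roughly 5% to 85% of any such bias would be removed, depending on when people leave. It is not a demonstrated problem. Even the most adverse illustration, 2.7 points overall, is about half of one SE (2.7/5.59 = 0.48), or a third with the larger SD (2.7/7.91 = 0.34).

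**What to change.** In the Statistical Analysis section:

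1. Fit the planned model (dose, form, group and interactions) as a linear mixed model to AUCs from all completed test days, including those of participants who later withdraw.
2. Include a participant random effect and a covariance that lets response differ between participants, for example participant-by-dose and participant-by-form terms. State a simpler fallback in case these cannot be estimated with about 20 people.
3. Derive the primary % reduction from the model means, as 100 × (1 − mean at the dose / mean at 0 g of the same form), with a confidence interval. This matters because a participant who leaves before a 0 g day has no individual % reduction.
4. Keep Tukey's test for the pairwise comparisons.
5. Report completers of all six visits as a sensitivity analysis, with the number of test days per treatment and the reason and last visit for each withdrawal.

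The cost is a few sentences of text. No visits, samples or participants are added.
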